Aware Treatment: Aware Recovery Care (ARC) is an in-home addiction treatment program that provides highly intensive, rigorously monitored, 52 weeks of intensive outpatient care, based on a chronic disease model of care. The approach implements principles of evidence-based practices including Motivational Interviewing, Cognitive Behavioral Therapy, and Dialectical Behavioral Therapy. Additionally, all families are offered education and the opportunity to participate in the treatment process. The client's individualized treatment team consists of a licensed professional (nurse or master's level clinician), two Certified Recovery Advisors (CRAs), and an LMFT. The clients care team is overseen by a master's level alcohol and drug counselor, an advanced practicing nurse, and an addiction psychiatrist. The licensed professional is responsible for leading the team, collaborating with external providers, communicating with family members and providing referrals to external providers as needed. The CRAs are lived-experience advisors, at least one of whom is both age and gendered match in order to provide a more intimate therapeutic relationship. CRAs are responsible for delivering a staged biopsychosocial curriculum. Familial involvement is another key component of this model, with education and frequent communication provided. All care teams include a Licensed Marriage and Family Therapist for 6 family therapy sessions, as well as 4 family education sessions delivered by a special trained family education facilitator.

Randomization. At the randomization visit, the research assistant will conduct assessments to evaluate alcohol use. Eligible patients will be assigned to one of the two groups using randomization sequence. The randomization sequence will allow for equal representation between two groups without bias on gender, age or ethnicity given all individuals will be categorized as single variable

Assessments:

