We are planning to assess a broad range of subject characteristics, process measures and treatment outcomes over the 3-month trial and at the 6 week post treatment follow-up (See Table 1). Baseline assessments are designed to ensure that patients meet eligibility criteria and that important predictor variables such as cognitive impairment are assessed. Baseline measures include evaluation and understanding of the extent of the AUD issue from a several different vantages points. Primary outcome measures include reductions in days per week of use and negative BAU screens for alcohol. Monthly assessments will take approximately 30 minutes and monthly and follow-up's 45 minutes. Patients will be paid \$10 for the baseline and monthly assessments, \$25 for follow-up assessments (up to \$65 total).

active alcohol use disorders.

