2) direct entry of most data at time of collection; and 3) utilization of on-line error- checking procedures. The PI supervises data procedures. All error corrections are fully documented in the research records of the study. All research personnel are required to participate in and document training in protection of human subjects and the responsible conduct of scientific research. Data entry and review in this study will be conducted using a web-based data collection and monitoring system. Another set of automatic email reports, sent on a weekly or less frequent basis, provides a set of designated recipients (e.g., the PI or Project Director) with information about study logistics, such as number of subjects enrolled, number of subjects active in the protocol, gender composition of the sample, percentage of missing data by each assessment instrument, or any other information necessary to monitor the progress of the project and the compliance with the protocol. A fully computerized system allows this type of monitoring without furnishing investigators with data that could influence the outcome of the study. The system meets the highest security and reliability standards. All connections to the systems are secured and encrypted using 128-bit strong encryption protocols and only authorized users are able to access the system.

5. Genetic Testing N/A ⊠

- **A.** Describe
 - i. the types of future research to be conducted using the materials, specifying if immortalization of cell lines, whole exome or genome sequencing, genome wide association studies, or animal studies are planned *Write here*
 - ii. the plan for the collection of material or the conditions under which material will be received
 - iii. the types of information about the donor/individual contributors that will be entered into a database *Write here*
 - iv. the methods to uphold confidentiality Write here
- B. What are the conditions or procedures for sharing of materials and/or distributing for future research projects? *Write here*
- C. Is widespread sharing of materials planned? Write here
- D. When and under what conditions will materials be stripped of all identifiers? Write here
- E. Can donor-subjects withdraw their materials at any time, and/or withdraw the identifiers that connect them to their materials? *Write here*
 - i. How will requests to withdraw materials be handled (e.g., material no longer identified: that is, anonymized) or material destroyed)? Write here

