13. **Statistical Considerations:** Describe the statistical analyses that support the study design. A sample size of 110 would provide >80% power (α = .05) to detect a medium to large effect size (d= .65) and allow to fully evaluate gender differences. Greater power is provided by the repeated measures GEE and LMM analysis for the primary outcomes of BAC screen negative for alcohol drugs and days/month of self-reported illicit drug use. Sample size calculations for LMM are dependent on the number of repeated events, the retention rate, and the interclass correlation, in addition to the alpha level, the expected effect size, and the statistical power 198. The current randomized trial would provide estimates to guide a power analysis for a large Stage II study. Statistical procedures and models for analyzing data have been selected according to the research hypotheses being investigated and the types of data available. We will use α < .05, but will use appropriate corrections for multiple tests. Statistical analyses will be conducted on an intention-to-treat sample using SPSS. Using chi square and t-tests, we will first conduct preliminary analyses of the adequacy of the randomization procedure, the comparability of baseline measures for the two groups, and the possible need for covariates in the analyses of treatment outcome data.

SECTION II: RESEARCH INVOLVING DRUGS, BIOLOGICS, RADIOTRACERS, PLACEBOS AND DEVICES

ft
his
section
(or one
of its part
s. A or B
() is not
applicable.
check o
ff N/A
and de
lete the
rest of th
e section.

A.	RADIOTRACERS ⊠N/A	
1.	Name of the radiotracer: Write here	
2.	Is the radiotracer FDA approved? □YES	□NO

- If NO, an FDA issued IND is required for the investigational use unless RDRC assumes oversight.
- 4. **Background Information:** Provide a description of previous human use, known risks, and data addressing dosage(s), interval(s), route(s) of administration, and any other factors that might influence risks. If this is the first time this radiotracer is being administered to humans, include relevant data on animal models.

Check one: □IND# Write here or □RDRC oversight (RDRC approval will be required prior to use)

Write here

3.

4. **Source:** Identify the source of the radiotracer to be used. *Write here*

5. **Storage, Preparation and Use:** Describe the method of storage, preparation, stability information, method of sterilization and method of testing sterility and pyrogenicity.

Write here

R	DRUGS/BIOLOGICS

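### The power statement says 110 participants can fully evaluate gender differences, but on its own basis this does not hold for treatment effects by gender (about 66% power within one gender, about 39% for an assumed .65 SD interaction)

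*Combined protocol and SAP*

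**What the plan says.** Section I.13 (Statistical Considerations) opens with "A sample size of 110 would provide >80% power (α = .05", and the same sentence continues "to detect a medium to large effect size (d= .65) and allow to fully evaluate gender differences". It then says that GEE and LMM will add power for the primary outcomes. It notes that "Sample size calculations for LMM are dependent on the number of repeated events, the retention rate, and the interclass correlation", among other inputs, but gives no value for retention or correlation. Baseline tests are meant to show "the possible need for covariates in the analyses of treatment outcome data", so adjustment is left open.

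No other sentence describes a gender analysis. The three aims in Section I.1 do not mention gender. In Section I.4 it comes up in the matching of recovery advisors to clients, in the Randomization paragraph ("The randomization sequence will allow for equal representation between two groups without bias on gender, age or ethnicity") and in the monitoring reports, which track "gender composition of the sample". No gender hypothesis, model term or expected split is given.

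**The concern.** The gender clause shares a sentence with the sample size, alpha and effect size, so it reads as a property that the calculation delivers. In a two-arm device trial, a natural reading is that the trial can show whether the device works in men and in women, or works differently in them. Both questions need more information than the overall comparison. A within-gender test uses about half the participants, and at a 50:50 split the interaction contrast has twice the standard error of the overall contrast.

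At stake is how a gender result would be read. A non-significant interaction from a trial said to be sized for gender could be taken as evidence that the device effect is the same in both genders, when the estimate may be too imprecise to say so.

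**Working it through.** **Inputs from the documents.** N = 110, alpha = .05, d = .65 (Section I.13). Two arms with equal representation, so 55 per arm (Section I.4, Randomization). Three monthly assessments plus a six-week follow-up, so 3 or 4 post-baseline visits (Section I.4, Assessments).

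**Assumptions.** Two-sided test; interaction of .65 SD; gender split 50:50 or 30:70; dropout 0 or 20%; correlation r between any two visits of .3 to .9. The documents give none of these.

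**Method.** Power from the noncentral t distribution, with noncentrality .65/SE in SD units.

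**1. The plan's own figure.** SE = √(2/55) = .191; noncentrality .65/.191 = 3.41; power 92%. The stated figure of more than 80% is reproduced.

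**2. Men versus women, ignoring treatment.** At 50:50 the arithmetic is the same: 92%. At 30:70 (33 and 77 people), SE = √(1/33 + 1/77) = .208 and power is 87%.

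**3. Treatment effect within one gender, single endpoint, 50:50.** There are 27.5 per arm. SE = √(2/27.5) = .270; noncentrality 2.41; power 66%.

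**4. Treatment-by-gender interaction, single endpoint.** SE = √(2/a + 2/b), where a and b are the numbers per arm in each gender.

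| Split | Dropout | a, b | SE | Power |
|---|---|---|---|---|
| 50:50 | 0 | 27.5, 27.5 | .381 | 39% |
| 30:70 | 0 | 16.5, 38.5 | .416 | 34% |
| 50:50 | 20% | 22, 22 | .426 | 33% |
| 30:70 | 20% | 13.2, 30.8 | .465 | 28% |

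At 50:50 with no loss, the 95% CI half-width is 1.983 × .381 = .76 SD, wider than the planned effect. By the normal approximation, 80% power needs N = 16 × (1.960 + .842)²/.65² ≈ 298.

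**5. Interaction with repeated measures, 50:50, no loss.** Averaging k visits multiplies the variance by f = (1 + (k − 1)r)/k. Baseline adjustment changes this to f − r². A constant effect over visits is assumed.

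| k | r | f | Unadjusted | f − r² | Adjusted |
|---|---|---|---|---|---|
| 3 | .3 | .533 | 64% | .443 | 72% |
| 3 | .5 | .667 | 54% | .417 | 74% |
| 3 | .7 | .800 | 47% | .310 | 86% |
| 3 | .9 | .933 | 42% | .123 | over 99% |
| 4 | .3 | .475 | 69% | .385 | 78% |
| 4 | .5 | .625 | 57% | .375 | 79% |
| 4 | .7 | .775 | 48% | .285 | 89% |
| 4 | .9 | .925 | 42% | .115 | over 99% |

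Within the assumed range, the adjusted analysis passes 80% at r of about .62 (three visits) or .54 (four visits). The unadjusted analysis does not reach 80%. At 30:70 with 20% dropout, the unadjusted case with k = 3 and r = .9 falls to about 30%.

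**The case against.** The case for the plan has four parts.

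- **The clause may mean men versus women overall.** Its words allow that, and power is then 92% (87% at 30:70). This stands, and it is why the point is confined to treatment effects by gender.
- **The planned analysis is repeated-measures, not a single endpoint.** This also stands in part. At 50:50 with no loss, within-gender power for the mean of three to four visits is 69–93% unadjusted and at least 94% with baseline adjustment. The interaction can pass 80% with adjustment. But the power sentence is not built on those inputs, and adjustment is not committed to. In the smaller gender at 30:70, unadjusted within-gender power is 47–75%.
- **The .65 SD interaction is not the plan's.** True. It asks for a gender difference as large as the whole planned effect, which is generous. At half that size (.325 SD), single-endpoint power is about 13%.
- **The trial is preliminary.** Its title says so, and Section I.13 says that it will inform a larger Stage II study. No aim depends on gender. That limits the harm, but it sits poorly with a claim of full evaluation.

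Three stronger readings are tempting. A reader might infer that the trial is underpowered overall; the 92% rules that out on the plan's inputs. A reader might infer that the planned model cannot reach 80% for gender; the documents do not settle that, since correlation, retention and adjustment are open. A reader might also take 42% and over 99% as the limits of interaction power. They are not limits. The 42% assumes an even split and no loss, and the upper figure needs a correlation near .9 plus baseline adjustment.

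**Conclusion.** The overall power statement is correct. The attached gender claim is wrong as written for treatment effects by gender, because the stated N, alpha and effect size do not give the trial that property. On the sentence's own basis, power is about 66% within one gender and about 39% for the interaction, at the most favourable split and with no loss. These figures rest on a two-sided .05 test, and the interaction figure also on the assumed .65 SD. A multiplicity correction, which Section I.13 promises without detail, would lower them. The repeated-measures model may recover some or all of the shortfall, but the plan does not show that it does.

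The unstated split, retention and correlation are missing detail rather than errors in themselves. Severity is minor: no aim rests on gender, and the primary comparison is unaffected.

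**What to change.** Delete the gender clause from the power sentence in Section I.13 and limit the sentence to the overall treatment effect. Suggested text:

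*With 110 participants (55 per arm) the trial has more than 80% power at two-sided alpha .05 for an overall treatment effect of d = .65. Any analysis by gender is exploratory and will be reported as a treatment-by-gender estimate with its 95% confidence interval on the self-reported use outcome.*

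The self-reported outcome is named because Group 2 has no device (Section I.4, Aware/Group 2), so device BAC results exist only in Group 1 and allow no treatment-by-gender contrast. That outcome is described differently in Section I.4 ("Primary outcome measures include reductions in days per week of use and negative BAU screens for alcohol") and Section I.13 ("days/month of self-reported illicit drug use"). Reconciling the two is a separate matter, but the final text should use whichever definition is adopted.

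The cost is one clause removed and one sentence added, with no extra participants or visits. The downside is a less favourable claim about gender.

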HRP-503B – BIOMEDICAL RESEARCH PROTOCOL (2017-1)

Protocol Title: Preliminary Effectiveness of Remotely Monitored Blood Alcohol Concentration Device as Treatment Modality

Principal Investigator: [name].

Version Date: June 1, 2020

(If applicable) Clinicaltrials.gov Registration #: NCT04380116

INSTRUCTIONS

This template is intended to help investigators prepare a protocol that includes all of the necessary information needed by the IRB to determine whether a study meets approval criteria. **Read the following instructions before proceeding:**

- 1. Use this protocol template for a PI initiated study that includes direct interactions with research subjects. Additional templates for other types of research protocols are available in the system Library.
- 2. If a section or question does not apply to your research study, type "Not Applicable" underneath.
- 3. Once completed, upload your protocol in the "Basic Information" screen in IRES IRB system.

SECTION I: RESEARCH PLAN

1. **Statement of Purpose:** State the scientific aim(s) of the study, or the hypotheses to be tested. The purpose of the current study is to evaluate the usage and acceptability of the Soberlink's blood alcohol concentration (BAC) unit in collaboration with Aware treatment to assess increased sobriety within patients suffering from alcohol use disorder (AUD).

The specific AIMS will be:

- 1) To determine the effectiveness of Soberlink's ability to increase abstinence
- 2) To evaluate the impact of Soberlink's device on the participant based on their quality of health and sobriety.
- 3) To evaluate the extent to which need for higher levels of follow-up care and treatment is reduced for individuals who have had access to the Soberlink device.
- 2. **Probable Duration of Project:** State the expected duration of the project, including all follow-up and data analysis activities.

The duration of the time of the study will be two years to complete. This will include (as seen on Figure 1) time for IRB approval and recruitment, randomization and completion the study, follow-up and lastly analysis with dissemination.

[figure not shown]

Figure 1: Overview and Timeline

3. **Background:** Describe the background information that led to the plan for this project. Provide references to support the expectation of obtaining useful scientific data.

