Individuals who miss two consecutive BAC's will be followed up by either Research Assistant or the PI. Individuals who miss four consecutive BAC's without contact of the PI or the research assistant will be temporarily hold unless the individual has expressed thoughts of leaving the study prematurely. Missing more than six consecutive BACs without communication will result in termination from the study by the PI. A pilot study contacted at Aware prior to the PI being involved demonstrated little reactivity or premature departure for those who had access to the Soberlink device.

Aware/Group 2:

This group will not receive access or training to Soberlink device, however they will be recruited to complete the same set of surveys at the same time intervals (See Figure 2). Upon completion of the surveys, the participants in group 2 will be paid, and told reminded the subsequent follow-ups. Reminder emails (see attached reminder emails) will be sent out the day before, and the day of the 1 month, 2 month and 3 month evaluations. Subsequent phone calls will be made by the research assistant to the participant if they have missed their evaluation. The estimated time of the process will take under 30 minutes to complete.

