Table 1. List of Assessments Screening & Baseline Assessments a) Generalized Anxiety Disorder (GAD-7) will be used to assess for generalized anxiety The Structured Clinical Interview for DSM-V (SCID) will be used to assess lifetime and current DSM- V substance use and Axis I and II psychiatric disorders ¹⁸¹ and screen patients for psychiatric eligibility. c) Patient Health Questionnaire (PHQ-9) will be used for depression symptoms for the past 2 weeks. d) Substance Use History will assess frequency, intensity and duration of use and route of administration of drugs. e) Alcohol Abstinence Self-Efficacy Scale will evaluate the participant's beliefs of alcohol usage. Outcome Measures. a) Soberlink (BAC): sensor to detect alcohol levels at an accuracy of +/-.005 BAC. BAC is established by the manufacturer based on predetermined cut off points b) The Time Line Follow Back (TLFB), administered by research administer onto a secure webserver. Will be used to collect self-reported frequency, quantity and route of administration of prescription opioids, cocaine, alcohol and other drugs use during the preceding 30 days, and use 185-187 Quality of Life Scale is a self-directed survey that assess the quality of life of the individual. d) Soberlink Use Survey is a self-directed survey that evaluates the effectiveness of the device. e) The Drug Risk Response Test (DRRT) ^{189,190} is a role-playing assessment of coping responses to drug use risk situations, and takes 8-10 minutes to complete. The instrument is composed of six audio-taped scenarios. Patients are instructed to imagine that they are in the situation and provide a detailed account to how they would respond to that situation. Patient accounts are recorded and scored by trained evaluators. The instrument provides 4 measures: the number of coping responses, the number of activities per response, the quality of the best response and the

Data monitoring procedures involve an organizational structure of clearly defined tasks assigned to all research personnel involved in the conduct of this study. The organizational structure used to ensure quality of data in this project include: 1) extensive training and close supervision of research assistants in data collection;

f) AUDIT C- is brief alcohol screen that reliably identifies patients who are hazardous drinkers or have

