- F. Describe the provisions for protection of participant privacy Write here
- G. Describe the methods for the security of storage and sharing of materials Write here
- 6. **Subject Population:** Provide a detailed description of the types of human subjects who will be recruited into this study.
 - We will recruit 110 individuals with alcohol use disorder as diagnosed by the DSM-5. They will be recruited at Aware Recovery Center in North Haven, CT.

7.	Subject classification: Check off all classifications of subjects that will be specifically recruited for enrollment in
	the research project. Will subjects who may require additional safeguards or other considerations be enrolled
	in the study? If so, identify the population of subjects requiring special safeguards and provide a justification
	for their involvement.

for their involvement.	the population of subjects requir	ing special safegualus and provide a justification
⊐Children	☐ Healthy	□Fetal material, placenta, or dead fetus

APPROVED BY THE YALE UNIVERSITY IRB 6/9/2020

IRB# 2000027787

□Non-English Speaking	☐ Prisoners	☐Economically disadvantaged persons
□Decisionally Impaired	☐ Employees	☐Pregnant women and/or fetuses
□Yale Students	☐ Females of childbearing pote	ntial
NOTE: Is this research proposal o	designed to enroll children who a	are wards of the state as potential subjects?

8. Inclusion/Exclusion Criteria: What are the criteria used to determine subject inclusion or exclusion? Inclusion Criteria: 1) are at least 21 years old, 2) currently enrolled at Aware In home treatment, and 3) Primary or secondary DSM-5 diagnosis of alcoholism use disorder (AUD).

Exclusion Criteria: 1) Current suicide or homicide risk, 2) meet criteria for DSM-IV current psychotic disorder, or bipolar disorder, 3) does not have phone access with text message capabilities, 4) Unable to read or understand English, 5) Unable to complete the study because of anticipated incarceration or move, 6) Life-threatening or unstable medical problems, 7) No course of current or pending legal action, 8) Soberlink results being used for child custody or legal circumstance.

- 9. How will **eligibility** be determined, and by whom?

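### Section 13 words the self-report primary outcome as illicit drug days in an alcohol trial; it should name alcohol use, in the same words as the Assessments section

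*Combined protocol and SAP*

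**What the plan says.** The primary outcomes are worded in two places.

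- **Section I.13, Statistical Considerations:** the GEE and LMM analyses are for the primary outcomes of "BAC screen negative for alcohol drugs and days/month of self-reported illicit drug use".
- **Section I.4, Assessments:** "Primary outcome measures include reductions in days per week of use and negative BAU screens for alcohol". Shortly before, the same paragraph says "Baseline measures include evaluation and understanding of the extent of the AUD issue".

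The rest of the protocol sets the context.

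- **Section I.1:** the purpose is greater sobriety in patients with alcohol use disorder. Aim 1 is "To determine the effectiveness of Soberlink's ability to increase abstinence".
- **Sections I.6 and I.8:** all 110 participants are to have a DSM-5 alcohol use disorder, as a primary or secondary diagnosis, and to be at least 21.
- **Section I.4, Aware/Group 2:** "This group will not receive access or training to Soberlink device, however they will be recruited to complete the same set of surveys".
- **Table 1, Outcome Measures:** the TLFB collects self-reported "prescription opioids, cocaine, alcohol and other drugs use during the preceding 30 days".

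**The concern.** Participants are enrolled because of their drinking, and the question is whether the device helps them stop. Alcohol is not an illicit drug for adults of 21 or over, so illicit drug use, read literally, leaves out every drinking day.

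The other named primary, the device BAC, comes from equipment that Group 2 does not receive. Self-report is therefore the only named primary that can compare the arms. If it counts illicit drug days, the analysis written in Section 13 contains no between-arm comparison of drinking. The TLFB would supply the literal variable, so an analyst could follow the plan faithfully, obtain a clean result and still not answer the trial's question. With two wordings in force, the substance could also be chosen after the data are seen.

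**Working it through.** **1. The two wordings side by side**

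| Feature | Section I.13 | Section I.4, Assessments |
|---|---|---|
| Substance | illicit drugs | none attached to use |
| Unit | days per month | days per week |
| Form | days | reductions in days |

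**2. Substance.** In the Assessments sentence, alcohol is attached grammatically to the breath screens, not to days of use. The nearby reference to alcohol use disorder makes alcohol the natural reading. On that reading the section contradicts Section 13. On the other reading it leaves the substance open. Neither reading removes the word *illicit* from Section 13, and no other section corrects it.

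**3. Is the literal variable computable?** Yes. Neither section names the source of the self-report primary. The TLFB is the listed outcome measure described as recording frequency of use by substance, and it covers opioids, cocaine and other drugs alongside alcohol. Alcohol days are equally available. I assume that the TLFB is among the assessments both groups complete, since Group 2 has the same surveys at the same intervals.

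**4. Unit.** Taking a month as the TLFB's 30 days, days per week = (7/30) × days per 30 days = 0.233 × days per 30 days. The difference in means and the SD are both multiplied by 0.233, so d, the test statistic and the p-value are unchanged. This difference is harmless.

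**5. Form.** Section 13 plans repeated-measures models. These take days at each visit and can report a between-arm reduction over time, so *reductions* may only state the direction of benefit. If baseline is a covariate in a linear model, analysing change or follow-up level gives the same treatment estimate. The documents give no SD and no baseline to follow-up correlation, so I put no power figure on this difference.

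**6. Is the power statement affected?** Inputs from Section 13: N = 110, d = .65, α = .05. Assumptions: two-sided test, and 110/2 = 55 per arm (Section I.4, Randomization, describes equal representation).

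- Normal approximation: d × √(n/2) − 1.96 = .65 × √27.5 − 1.96 = 3.409 − 1.960 = 1.449, which gives power 92.6%.
- t-based calculation: 92.2%.

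The stated figure of more than 80% is reproduced. The d is standardised and tied to no named outcome, so correcting the substance leaves the statement as it is.

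**The case against.** The best defence is that the phrase is carried-over wording nobody would follow. It sits in a remark about power, the same sentence speaks of alcohol drugs, and the Assessments section is the dedicated outcome statement, in an alcohol context. This probably explains how the phrase arose. It does not correct it: Section 13 is where an analyst looks for the primary outcome, and the literal reading can be carried out.

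A second defence is that drug days were intended. Alcohol use disorder may be a secondary diagnosis, Aware treats substance use disorder generally, the TLFB records other drugs, and Aim 1 speaks of abstinence without naming alcohol. That is a fair reason to keep non-alcohol drug days as an outcome. It does not make them an answer to a purpose stated in terms of alcohol use disorder.

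It is also fair to say that the unit and form differences count for little. A reader might infer that the two wordings imply very different power, because unadjusted change and follow-up level can have different standardised effects. The documents do not support that. It would need an assumed correlation, equal SDs and a single-time-point t-test, whereas the plan is GEE and LMM.

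**Conclusion.** The point holds for the substance. Section 13 names illicit drugs where the trial's purpose requires alcohol, and the Assessments section does not settle the matter. It is more than clerical, because self-report is the only named primary available in both arms and the mislabelled variable can be computed.

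A reader might go further and infer that the trial cannot compare drinking between its arms. The documents do not support that: the Assessments wording can be read as alcohol days, and the TLFB records alcohol. Nor do they support a claim that the sample size is wrong. Power is about 92% at d = .65, with 55 per arm and a two-sided test assumed, and it stays there after the correction. The absence of device BAC in Group 2 matters here only because it leaves self-report as the shared primary; it is otherwise a separate issue.

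**What to change.** 1. In Section I.13, replace illicit drug use with alcohol use, and correct alcohol drugs to alcohol in the same sentence.
2. Use the identical definition in Section I.4, Assessments. For example: *days of any alcohol use in the past 30 days by TLFB, Group 1 vs Group 2, in the repeated-measures model already planned*.
3. State that *reductions* is the direction of benefit. If change from baseline is meant, say so in both places.
4. If non-alcohol drug days are wanted, name them as a separate outcome, with their rank stated by the investigator.

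The cost is wording in two sections and two short decisions by the investigator: the meaning of *reductions*, and whether and at what rank to keep drug days. The TLFB already records alcohol, so no new instrument or change in sample size is needed. The edit should be made before outcome data are compared by arm. It does not address the missing device BAC in Group 2.
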